1.3 Exploratory Objectives

- To determine Progression Free Survival and Overall Survival of nivolumab monotherapy and of nivolumab combined with ipilimumab in patients with advanced solid tumors with detectable POLE or POLD1 mutations as determined by plasma cfDNA, and in all treated patients (detectable mutations in tissue or plasma cfDNA).
- To determine the correlation between POLE or POLD1 mutations occurring within or outside of the exonuclease domain and tumor mutation load as determined by whole exome and RNA sequencing.
- To determine the correlation between tumor mutation burden assessed in plasma cfDNA and assessed directly in tumor tissue.

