- 1 Bloodwork Timing: Pre-treatment blood draws may be done the day prior to treatment if necessary, and when treatment is to begin on a Monday, may be done on the previous Friday (maximum 72 hours prior to treatment). In order to ensure that nadir counts are not missed, every effort should be made to do interim blood draws within 24 hours of the day specified in the protocol.
- 2 Confirmation that the patient would meet the requirements for randomization (CBC with differential, serum creatinine, bilirubin, and AST&/or ALT only). These lab results may be ascertained based on patient chart review. It is not necessary to repeat these labs prior to the screening step for the purposes of this study, if results already available within the previous 28 days.
- 3 It is preferable that both amylase and lipase are assessed. For sites where only 1 of these parameters is routinely measured then either lipase or amylase is acceptable.
- 4 Free T3 and free T4 will be measured if TSH is abnormal.
- 5 To be done additionally every 3 months thereafter to follow abnormal lab results felt related until resolved to  $\leq$  Grade 2.
- 6 Women of child-bearing potential only (urine or serum test). Must be performed within 72 hours prior to administration of study drug. To be done every 4 weeks when on-study.
- 7 Tumor markers including CEA, CA-125, CA-19-9, etc., as indicated per standard of care testing for primary tumor. If elevated at baseline, will be monitor serially. If not elevated at baseline, will not be monitored serially.
- 8 Studies at time of progression at the discretion of patients and treating physician if feasible (optional).
- 9 To be done every 12 weeks until relapse or progression (iCPD) for up to 2 years, for patients with CR/ICR, PR/iPR, SD/iSD response as defined in Section 8.0. For patients with iUPD, confirmatory scans must be performed at least 4 weeks, but no longer than 8 weeks, after iUPD was identified.
- 10 First tumor assessment should be performed 12 weeks ( $\pm$  1 week) following randomization. To ensure comparability, baseline scans and subsequent scans to assess response must be performed using identical technique (i.e. scans performed immediately following bolus contrast administration using a standard volume of contrast, the identical contrast agent, and preferably the same scanner). Maintain schedule every 12 weeks even if cycles are delayed.

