6.3 Registration and Randomization

Registration and Randomization will be provided electronically.

Note: The validity of results of the trial depends on the authenticity of and the follow-up of all patients entered into the trial. Under no circumstances, therefore, may an allocated patient's data be withdrawn prior to final analysis, unless the participant withdraws from the trial and requests that data collection/submission cease from the point in time of withdrawal.

All eligible patients admitted to the trial will be followed by the coordinating center. It is the responsibility of the physician in charge to satisfy himself or herself that the patient is indeed eligible before requesting registration.

All randomized patients are to be followed until death or until sites are informed by CCTG that further follow-up is no longer required. The follow-up requirements for ineligible patients are outlined in Section 5.1.

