**7.2 Duration of Therapy**

Patients should continue on trial treatment until RECIST 1.1/iRECIST defined progression or unacceptable toxicity or other treatment discontinuation criterion is met (see below).

An individual patient will not receive any further investigational product if any of the following occur in the patient in question:

- Patient request.

- Lost to follow-up.
- Patient is determined to have met one or more of the exclusion criterion for the trial.
- Participation at trial entry and continuing investigational therapy might constitute a safety risk.
- Pregnancy or intent to become pregnant.
- Initiation of alternative anti-cancer therapy including another investigational agent.

There is no maximum duration of treatment as patients may continue to receive investigational product beyond RECIST 1.1/iRECIST defined progression as long as they are continuing to show clinical benefit. In such cases, patients may continue to receive treatment following objective progression at Investigator's discretion and as agreed with the patient.

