10.4 Follow-up Off Protocol Treatment

All patients will be seen at 4 weeks after completion of protocol therapy. Continued follow-up required for all patients every 3 months to collect information on ongoing toxicities, late toxicities (including second malignancies) and survival data. This follow-up will continue until death or conclusion of the trial.

PROTOCOL DATE: 2018-MAY-30

CRI-CCTG: 0001

CCTG: IND.235

For patients who go off protocol treatment with CR/ICR, PR/iPR, SD/iSD or iUPD ongoing, tumor assessments will be required every 3 months until relapse (see Section 5.0 for investigations to be performed). Please note for patients who go off protocol treatment with iUPD, confirmatory scans should be performed at least 4 weeks, but no longer 8 weeks, after iUPD was documented.

A Death report will be required on all patients. Due within 2 weeks of knowledge of death (see Appendix IV- Documentation for Study).

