PFS and OS of nivolumab monotherapy and of nivolumab combined with ipilimumab in patients with advanced solid tumors with detectable mutations as determined by plasma cfDNA, and in all treated patients (detectable mutations in tissue or cfDNA) will be evaluated as exploratory endpoints.

Kaplan-Meier method will be used to estimate probabilities of OS and PFS for each arm. Patients alive at the time of trial analysis will be censored as of the date of their last disease assessment. Medians and 90% CI will be provided, if available. No formal comparisons will be made between the two arms. Adjusted analyses will be also consider mutational load as one of the covariates.

Tumors will undergo whole exome and RNA sequencing to evaluate the genetic landscape of mutated tumors in responders versus non-responders to immune checkpoint blockade.

Detectable mutations in the initial study population are *POLE*/*POLD1* mutations based on plasma cfDNA.

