## APPENDIX IV - DOCUMENTATION FOR STUDY

Follow-up is required for patients from the time of registration and will apply to all eligible and ineligible patients. This trial will use a web-based Electronic Data Capture (EDC) system for all data collection including SAE reporting (see Section 9.0 for details regarding SAE reporting). For details about accessing the EDC system and completing the on-line Case Report Forms, please refer to the Data Management Guidebook posted on the CRI-CCTG-0001 area of the CCTG web-site ([www.ctg.queensu.ca](http://www.ctg.queensu.ca)).

The ELECTRONIC CRFs to be used in this trial are:

Electronic Case Report Form	To be Completed/Submitted Electronically:	Supporting Documentation to be sent using Supporting Document Upload Tool*
PATIENT REGISTRATION AND ENROLLMENT	At the time of patient registration and enrollment (see ENTRY/REGISTRATION PROCEDURES).	Copy of the screening consent form signature page, if enrolled based on POLE/POLD1 mutation by tumor tissue testing, copy of report with results, copy of report from plasma cfDNA testing performed at screening.
BASELINE REPORT	Due within 2 weeks of patient registration.	Copies of signature pages of main, and optional consent forms; relevant pathology & radiology reports.
TREATMENT REPORT	To be completed every 6 weeks (i.e. after each cycle). Due within 2 weeks of end of course. This report documents treatment, adverse events, investigations and response assessment for each course.	Relevant radiology reports.
CORRELATIVE STUDIES	See Section 12.0.	
END OF TREATMENT REPORT	To be completed when patient goes off protocol treatment. Due within 2 weeks of end of protocol treatment.	
4 WEEK POST TREATMENT REPORT	To be completed once on all patients, 4 weeks after going off protocol treatment. Due within 2 weeks after contact with patient.	Relevant radiology reports.
FOLLOW-UP REPORT	Follow-up Report to be completed every 3 months until death or conclusion of trial. Due within 2 weeks after contact with patient.	Relevant radiology reports.
RELAPSE/PROGRESSION REPORT	To be completed at the time of disease relapse or progression. Due within 2 weeks after contact with patient.	Relevant radiology reports.
DEATH REPORT**	Required for all patients while study is open. Due within 2 weeks of knowledge of death.	Autopsy report, if done.

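### Overall survival (OS) is given the progression-free survival (PFS) censoring date: living patients are censored at their last disease assessment, so the Kaplan-Meier OS estimate is biased downward

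*Combined protocol and SAP*

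**What the plan says.** Section 1.3 lists as an exploratory aim "To determine Progression Free Survival and Overall Survival of nivolumab monotherapy and of nivolumab combined with ipilimumab". Section 13.2 says Kaplan-Meier estimates will be produced for OS and PFS in each arm, with medians and 90% confidence intervals, and that "No formal comparisons will be made between the two arms". The only censoring rule for these two endpoints follows in the same paragraph: "Patients alive at the time of trial analysis will be censored as of the date of their last disease assessment". It is triggered by being alive and does not distinguish the endpoints. No other section gives a censoring date for OS.

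Two follow-up streams run with different end points:

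- **Tumor assessments.** Section 5.0, footnote 9: "To be done every 12 weeks until relapse or progression (iCPD) for up to 2 years". Section 10.4 requires them off treatment only until relapse.
- **Survival.** Section 6.3: "All randomized patients are to be followed until death or until sites are informed by CCTG that further follow-up is no longer required". Section 10.4: "Continued follow-up required for all patients every 3 months to collect information on ongoing toxicities, late toxicities (including second malignancies) and survival data". Appendix IV, on the death report: "Required for all patients while study is open".

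**The concern.** For OS, a living patient's follow-up should end when the patient was last known to be alive. Under this rule it ends at the last disease assessment, which for most patients who have progressed is around the progression scan. Deaths after that scan are still reported and counted at their true date. Time after progression is thus kept for those who die and discarded for those who live, so censoring depends on the outcome being estimated. Risk sets at later times are too small for the deaths they contain, the hazard is overstated, and the survival curve falls too low.

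Each arm's estimate is to be read on its own, so no between-arm contrast exists in which a common bias might partly cancel. Nor need the bias be equal in the two arms, since it grows with the number of patients alive after progression.

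**Working it through.** **One patient.** Suppose progression occurs at month 4. With scans every 12 weeks (2.8 months) it is seen at week 24 (5.5 months). A confirmatory scan 4 to 8 weeks later falls at weeks 28 to 32 (6.4 to 7.4 months). If the patient is alive at month 20, OS is censored at about month 5.5 to 7.4. If the patient dies at month 10, the event counts at month 10.

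**Inputs from the documents.** Scans every 12 weeks until progression, up to 2 years (5.0); accrual of about 24 months and 50 patients per arm (13.3); deaths and survival status collected throughout (6.3, 10.4, Appendix IV). The plan states no OS figure, so there is none to reproduce.

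**Assumptions.** Exponential time to progression with median 4, 4 or 6 months, followed by exponential post-progression survival with median 8, 12 or 12 months; no death before progression; follow-up uniform over 6–30, 12–36 or 24–48 months.

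**True OS.** With rates λ1 = ln 2 / (median PFS) and λ2 = ln 2 / (median post-progression survival),

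S(t) = (λ1·e^(−λ2·t) − λ2·e^(−λ1·t)) / (λ1 − λ2).

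At 24 months:

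- 4/8: (2 × 0.125 − 0.0156) / 1 = 23.4%
- 4/12: (3 × 0.25 − 0.0156) / 2 = 36.7%
- 6/12: (2 × 0.25 − 0.0625) / 1 = 43.8%

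Solving S(t) = 0.5 gives medians of 14.17, 18.31 and 21.26 months.

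**Rule as written.** Kaplan-Meier on at least 300,000 simulated patients per scenario. Deaths before cut-off are kept at the death date. Living patients are censored at the progression scan or, if none, at the last 12-weekly scan before the earlier of cut-off and 24 months.

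| PFS / post-progression median (months) | True median OS | Follow-up 6–30 | 12–36 | 24–48 |
|---|---|---|---|---|
| 4 / 8 | 14.17 | 11.65 (−2.52) | 12.37 (−1.80) | 13.52 (−0.65) |
| 4 / 12 | 18.31 | 13.19 (−5.12) | 14.14 (−4.17) | 16.01 (−2.30) |
| 6 / 12 | 21.26 | 15.83 (−5.43) | 16.77 (−4.49) | 18.74 (−2.52) |

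| PFS / post-progression median (months) | True 24-month OS | Follow-up 6–30 | 12–36 | 24–48 |
|---|---|---|---|---|
| 4 / 8 | 23% | 5% | 9% | 17% |
| 4 / 12 | 37% | 7% | 13% | 24% |
| 6 / 12 | 44% | 13% | 21% | 32% |

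On these rounded figures, 24-month OS is too low by 18, 30 and 31 points at 6–30 months and by 6, 13 and 12 points at 24–48 months.

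**Patients affected.** Those alive at analysis with progression already seen on a required scan make up 31–42% at 6–30 months (about 15 to 21 of 50 per arm) and 9–20% at 24–48 months (about 4 to 10 of 50).

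**Control.** Censoring the same simulated patients at data cut-off recovers the true medians, so the shortfall comes from the censoring date.

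**A different model.** With exponential OS independent of progression, median PFS of 3 or 6 months, and analysis 6, 12 or 24 months after last entry, the rule is again low in every case: a true median of 12 months gives 9.1–11.4, 18 gives 11.1–15.4, and 24 gives 12.3–18.0. Repeating two of the 18-month cases with 50 patients per arm gives typical medians of 12.1 and 13.9 months.

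**The case against.** Five points can be made for leaving the rule alone.

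- **The term is undefined.** Visit examinations also document disease, and section 10.2 accepts progression documented clinically. On a broad reading the last assessment comes later. But section 10.1 uses the term for the assessment that follows unconfirmed progression, which it ties to imaging. The flowsheet also schedules no history and examination at the 3-monthly follow-up, so long survival after progression would still be lost. Only a reading in which any contact counts removes most of the bias, and the text does not support that.
- **Scanning may go on longer than modelled.** Section 7.2 says "patients may continue to receive investigational product beyond RECIST 1.1/iRECIST defined progression as long as they are continuing to show clinical benefit", a confirmatory scan may be added, and section 10.4 carries no 2-year limit. This reduces the bias. With an 8-week confirmatory scan and no 2-year limit, the 6–30 month medians rise to 12.1, 13.9 and 16.5. With 6 months of assessment past the progression scan for every patient, they are 13.1, 15.4 and 17.9 (24–48 months: 13.9, 17.0 and 19.7). All remain below the truth.
- **The remedy also falls short early.** Censoring at the last 3-monthly contact gives 13.6, 17.3 and 20.1 at 6–30 months. This stands. Even with the confirmatory scan and no 2-year limit, moving to the remedy raises the median by about 1.5 to 3.5 months at 6–30 months and 0.5 to 2.2 at 24–48 months.
- **Sampling error is large.** With 50 patients, the correctly censored median in the 4/12 case at 24–48 months ranges from about 14 to 23 months (5th to 95th percentile), wider than the bias. True, but the bias always runs in the same direction and the 90% interval makes no allowance for it.
- **OS is exploratory and could be corrected at reporting.** The first part stands and limits the importance of the point. A correction made after the data are seen would, however, be an unplanned departure from a rule the plan states.

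**Conclusion.** The concern holds. Followed as written, section 13.2 gives OS estimates that are too low in each arm. The direction follows from the rule together with the two follow-up schedules. The size rests on the assumed survival times and analysis date: about 2.5 to 5.4 months off the median with 6–30 months of follow-up, and 0.7 to 2.5 months with 24–48 months. It is smaller if patients continue to be scanned after progression. The last-assessment rule suits PFS; what is missing is a separate rule for OS. The consequence is confined to an exploratory endpoint. The primary response-rate analysis, the secondary endpoints, power and sample size are untouched. The text should be corrected, but the main conclusions of the trial do not depend on it.

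**What to change.** Replace the single censoring sentence in section 13.2 with two:

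1. OS is the time from randomization to death from any cause; patients not known to have died are censored at the date last known alive, taken from the 3-monthly survival follow-up.
2. For PFS, patients alive without progression are censored at their last disease assessment.

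The cost is those two sentences. Survival status is already collected every 3 months and a death report is already required for all patients, so no visit, form or data item is added. A survival-status sweep close to the data cut-off would reduce the small shortfall that remains at an early analysis, but it is optional.

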### 13.3 Sample Size and Duration of Study

Approximately 100 immunotherapy-naïve patients with *POLE* or *POLD1* mutations identified at study entry via either circulating tumor DNA (cfDNA) central testing or prior local tumor assessment (to be confirmed retrospectively in such patients via central cfDNA testing) will be enrolled to this open-label, randomized, non-comparative trial.

We hypothesize that for this analysis treatment with immunotherapy will show a clinically relevant ORR of > 30% with single agent nivolumab or > 50% with combination nivolumab + ipilimumab in patients with advanced solid tumors with detectable *POLE* or *POLD1* mutations.

A sample size of 50 evaluable patients in each arm will achieve 90% power to show a clinically meaningful ORR. These calculations assume a single agent  $p_0 < 13\%$ ,  $p_1 > 30\%$  and combination therapy  $p_0 < 30\%$ ,  $p_1 > 50\%$ . Both assume a two-sided  $\alpha$  and  $\beta$  of 0.10.

Additional enrollment of up to 20% will be permitted as needed to replace patients found to not demonstrate *POLE* or *POLD1* mutations on central cfDNA.

As additional blood-based assays become available, the study may be amended to include additional cohorts.

Patients will be accrued from approximately four cancer treatment centers in the United States and four cancer treatment centers across Canada over a period of approximately 24 months.

### 13.4 Safety Monitoring

Adverse events will be monitored on an ongoing basis by the central office and their frequencies reported bi-annually at investigators' meetings.

The trial may be discontinued if the trial is terminated by the data and safety monitoring committee (if applicable), the Food and Drug Administration (FDA), or other regulatory authorities.

Any unforeseen deaths or serious adverse events may, after a discussion between the Sponsor, principal investigator and investigators at other sites, prompt an interruption to trial accrual pending a full investigation into the circumstances surrounding the event.

13.5 Screening Monitoring

The estimated mutation rate in the screened population is 7-15% based on prior publications. The frequency of POL mutations detected in blood will be assessed after every 50 patients screened. If the frequency is < 5%, the screening approach will be reviewed by the trial committee to determine whether modifications to the protocol are required to improve the efficiency of screening by, for example, targeting specific tumor histologies or other approaches.

## 14.0 PUBLICATION POLICY

### 14.1 Authorship of Papers, Meeting Abstracts, Etc.

14.1.1 The results of this study will be published. Prior to trial activation, the chair will decide whether to publish the trial under a group title, or with naming of individual authors. If the latter approach is taken, the following rules will apply:

- The first author will be based on overall enrollment and scientific contribution.
- A limited number of the members of the Canadian Cancer Trials Group, Cancer Research Institute, BMS, PDGx and additional investigators from participating centers, may be credited as authors depending upon their level of involvement in the study.
- Additional authors, up to a maximum of 15, will be those who have made the most significant contribution to the overall success of the study. This contribution will be assessed, in part but not entirely, in terms of patients enrolled and will be reviewed at the end of the trial by the study chair.

14.1.2 In an appropriate footnote, or at the end of the article, the following statement will be made:

"A study coordinated by the Canadian Cancer Trials Group. Participating investigators included: (a list of the individuals who have contributed patients and their institutions)."

### 14.2 Responsibility for Publication

It will be the responsibility of the Study Chair to write up the results of the study within a reasonable time of its completion. If after a period of six months following study closure the manuscript has not been submitted, the central office reserves the right to make other arrangements to ensure timely publication.

#### Dissemination of Trial Results

CCTG will inform participating investigators of the primary publication of this trial. The complete journal reference and, if where publicly available, the direct link to the article will be posted on the Clinical Trial Results public site of the CCTG web site (<http://www.ctg.queensu.ca>).

### 14.3 Submission of Material for Presentation or Publication

Material may not be submitted for presentation or publication without prior review by the Cancer Research Institute, Columbia University and, the CCTG Senior Investigator, Senior Biostatistician, Study Coordinator, and approval of the Study Chair. Individual participating centers may not present outcome results from their own centers separately. Supporting groups and agencies will be acknowledged.

15.0 ETHICAL, REGULATORY AND ADMINISTRATIVE ISSUES

15.1 Regulatory Considerations

All institutions must conduct this trial in accordance with International Conference on Harmonization-Good Clinical Practice (ICH-GCP) Guidelines.

This trial is being conducted under a Clinical Trial Application (CTA) with Health Canada. As a result, the conduct of this trial must comply with Division 5 of the Canadian Regulations Respecting Food and Drugs (Food and Drugs Act).

This trial is being conducted under an IND or related arrangement in other countries and all applicable Laws, Regulations and Policies must be followed.

